#### 3.3 Power and sample size

The primary outcome is change in SBP between the two randomized assignments. Our power calculation is based on the 12-week means and variances from the DASH-Sodium trial, where the 12-week between-group difference in SBP was -8.9 mm Hg. With 75 people in each arm, we will have sufficient power to detect a difference in SBP of -5.8 mm Hg (type 1 error of 0.05, power of 0.85; assuming a standard deviation of 11.85 and 11.4 for control and intervention groups based on the DASH-Sodium trial). We will over-recruit up to at least 176 participants to account for a 15% attrition rate.

With respect to secondary endpoints, we will have sufficient power to detect small differences of 15% or less in the following secondary endpoints: wake-time SBP, BMI, cholesterol, triglycerides, and hemoglobin A1c. Regarding adherence, we will be able to detect changes of 13.0%–29.5% in self-reported fruit and vegetable intake, urine sodium and potassium, and 24-hour recall potassium. These differences are smaller in magnitude than the actual differences observed in prior trials.

#### 3.4 Secondary Pre-specified Subpopulations Analysis

We will repeat the primary analysis to evaluate the effect of the intervention within the following subpopulations:

- 1. Age (≥65 vs < 65 years)
- 2. Biologic sex (female or male) based on index participant
- 3. Meal preparer status of the index participant
- 4. Baseline body mass index (≥30 vs <30 kg/m^2)
- 5. Baseline hemoglobin A1c (5.7 to <6.5%, <5.7%)
- 6. Family size (single family versus more than 1 participant)
- 7. Baseline SBP (following the randomization scheme)

We will fit generalized estimating equations restricted to the strata of interest. Threeway interaction product terms will be used to assess effect modification by baseline characteristic. Note these analyses are contingent on having sufficient number of participants in each strata. The strata involving baseline SBP will be performed regardless of number, following our randomization scheme.

Other stratified or subpopulations analyses based on baseline characteristics may be performed for hypothesis generation beyond the main study.

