## 3 Primary Outcome: Seated Blood Pressure

#### 3.1 Randomization and primary analysis

Participants will be randomized using a permuted block scheme (sizes of 2, 4, or 6) through a randomization feature embedded in REDCap in strata of baseline BP (SBP 120 to <140 mm Hg or 140 to <150 mm Hg). Blood pressure will be used as a stratification variable to ensure that people with varying degrees of hypertension are evenly distributed between interventions.

Randomization assignments will follow a 1:1 ratio such that half of participants will be assigned to order home-delivered, low-sodium, DASH-patterned groceries with the assistance of a registered dietitian over a 12-week period. The other half will be assigned to self-directed grocery shopping. This group will receive a handout about the DASH diet and receive a \$500 monthly stipend for 3 months.

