#### 3.2 Primary analysis

Our primary comparison is the net effect of randomized assignment (dietitian-assisted vs. self-directed shopping) on office SBP from baseline to 3- (primary) and 6-months post-randomization. Office SBP will be based on the average of three visits at baseline (two screening visits and the randomization visit each with 3 measurements; nine measurements total), two 3-month follow-up visits (each with 3 measurements; six measurements total), and two 6-month follow-up visits (each with 3 measurements; six measurements total). We will first confirm that the residuals of office SBP are normally distributed (if not it will be log-transformed). Modeling will be performed using generalized estimating equation (GEE) models with a treatment-by-visit interaction term. We will perform an intent-to-treat analysis. The visit term will be used to compare changes between 3 months versus baseline, 6 months versus 3 months, and 6 months versus baseline with a product (interaction) term to compare changes across intervention. Models will be adjusted for ZIP code or baseline blood pressure in sensitivity analyses.

Our hypothesis is that 12 weeks of dietitian-assisted, home-delivered, low sodium, DASH groceries will lower office SBP compared to 12-weeks of self-directed grocery shopping. The null hypothesis is that there will be no difference in office SBP between the two intervention arms. The comparison between the two treatment groups will be performed by comparing the regression coefficient for treatment with zero (a two-sided alpha of <0.05 will be considered statistically significant for the primary comparison at 3-months.

For additional pre-specified sensitivity analyses and subgroups to assess effect medication, see below.

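### Effect modification by age, BMI, HbA1c and baseline SBP is assessed only through two-level strata; a pre-specified continuous interaction would be a stronger test of graded modification

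*SAP*

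**What the plan says.** SAP section 3.4, Secondary Pre-specified Subpopulations Analysis, lists seven baseline characteristics. Three are categorical by nature or as defined: sex, meal preparer status and family size. The other four are measured on a continuous scale but appear only as two groups. The age entry begins "Age (≥65 vs < 65 years", BMI is cut at 30 kg/m², HbA1c at 5.7%, and baseline SBP follows the randomisation strata, which SAP 3.1 sets at 120 to <140 and 140 to <150 mm Hg.

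The GEE models are fitted within each stratum, and three-way "interaction product terms will be used to assess effect modification by baseline characteristic". No sentence says whether the covariate in that product term is the group indicator or the measured value. The list and the stratum-restricted models point to the indicator.

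The section adds: "Note these analyses are contingent on having sufficient number of participants in each strata". It gives no minimum number. The sentence after it exempts baseline SBP, whose strata are analysed whatever their size.

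The SAP gives no expected subgroup sizes, no baseline distributions and no power for any interaction.

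**The concern.** Interaction tests in a trial sized for a main effect have little power to begin with. Replacing a measured modifier by a two-group indicator reduces it further when the effect changes gradually, and the reduction is greatest when one group is small. BMI and HbA1c are analysed as continuous when they are outcomes (SAP 4.2), so the cut is a choice and not a limit of the data. SAP 3.1 explains the 140 mm Hg boundary as a means of balancing allocation. It does not argue that the effect changes there.

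The stratum-size condition adds a second problem. Because no number is fixed, whether age, BMI and HbA1c are examined at all is left to a later judgement. An interaction with the continuous value does not depend on a stratum count.

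At stake is how well the trial can show whether the intervention works differently across these characteristics. The primary comparison is not at stake.

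**Working it through.** **1. Inputs from the SAP.**
- Primary comparison: "a two-sided alpha of <0.05 will be considered statistically significant for the primary comparison at 3-months". The same level is assumed here for the interaction tests, since none is given for them.
- Sample size: "With 75 people in each arm, we will have sufficient power to detect a difference in SBP of -5.8 mm Hg".
- Error rates: "type 1 error of 0.05, power of 0.85".
- Spread: "assuming a standard deviation of 11.85 and 11.4 for control and intervention groups".
- Allocation: "Randomization assignments will follow a 1:1 ratio".

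**2. The plan's own figure.** Pooled SD = √[(11.85² + 11.4²)/2] = 11.63. With 75 per arm and a difference of 5.8, power is 0.863 by the normal approximation and 0.859 by the t test, against 0.85 stated. The stated calculation reproduces.

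**3. Scale of an interaction at N = 150.** With a continuous covariate, the effect change per SD of covariate that is detectable with 80% power is (1.96 + 0.84) × 2 × 11.63/√150 = 5.3 mm Hg. With a 50/50 cut, the detectable difference between the two subgroup effects is 10.6 mm Hg. With a 20/80 cut it is 13.3 mm Hg. Power is modest in every case.

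**4. Information kept by a cut.** For linear modification by a normal covariate, the share kept is φ(z_p)²/[p(1 − p)], where p is the share of participants in one group. Example at p = 0.10: 0.1755²/0.09 = 0.342, a loss of 66%. If the continuous test has 80% power, the cut test has Φ[(1.96 + 0.84)√(share kept) − 1.96].

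| Smaller group | Information lost | Power of cut test when continuous test has 80% |
|---|---|---|
| 50% | 36% | 61% |
| 30% | 42% | 57% |
| 20% | 51% | 50% |
| 15% | 57% | 45% |
| 10% | 66% | 37% |
| 5% | 78% | 26% |

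Simulation at N = 150 gave 61%, 46% and 33% for the cut at 50%, 20% and 10%, against 78–80% for the continuous term.

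**5. By variable, under assumed distributions.** Losses were:
- BMI: 36–50%.
- HbA1c: 35–52%.
- Age: 48–60% if 12–22% of participants are 65 or over, and 72% if only 6% are.
- Baseline SBP: 33% if uniform over 120–150, and 65% if 8% are at 140 or above.

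**6. Baseline SBP in more detail.** Assume a normal distribution with mean 130 and SD 10, truncated to 120–150. The truncated mean is 132.3 and the SD 7.21. About 16.6% are at 140 or above, which is 25 of 150 people. The cut keeps 51% of the information. With residual SD 11.6, the standardised interaction is slope × 7.21/(2 × 11.6/√150), multiplied by √0.51 for the cut. For a slope of 0.3 this is 1.14 (continuous) and 0.82 (cut).

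| Change in effect per 10 mm Hg of baseline | Cut, simulated power | Continuous, simulated power |
|---|---|---|
| 3 mm Hg | 12% | 20% |
| 5 mm Hg | 26% | 45% |

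Type I error was near 5% for both tests.

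**7. The reverse case.** Under the same distribution, with an effect that steps by 10 mm Hg at 140, the cut test has 48% power and the continuous test 28%. At a 50/50 split in the general simulation, a true threshold gave 78% for the cut and 58% for the continuous term.

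**The case against.** Four points on the other side deserve weight.

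- The advantage of the continuous term depends on the shape of the modification. If the effect changes at the cut, the cut test is better, as step 7 shows. The protocol (section 10) labels 140 to <150 mm Hg as stage II hypertension and stratifies on it, so an analysis by that stratum follows the design. This stands. It is a reason to keep the stratum analysis of SBP, but not to make it the only one.
- The slopes are assumed. Centred on an average effect of −5.8, a slope of 5 per 10 mm Hg implies about +0.3 at a baseline of 120 and −14.7 at 150, so it sits at the edge of what is plausible. At 3 per 10 mm Hg neither test has useful power. This stands too: the gain is relative and does not make these tests well powered.
- With baseline SBP also an outcome row in the GEE, a three-way term in continuous baseline SBP might seem ill-defined. It is not: in a fitted check, a GEE including that row gave the same three-way estimate and standard error as a regression of the change score.
- These are secondary analyses, and restricting subgroup models to adequate cell sizes is ordinary practice. That is true of stratum estimates, but it is no reason to withhold a continuous interaction test.

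A reader might also infer that the baseline SBP test could be dropped for small numbers. The SAP expressly rules that out. Nor do the documents show that a cut at 65 years or 140 mm Hg will give very unequal groups, since they report no baseline distribution.

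**Conclusion.** The concern holds as a limited point about secondary analyses. As written, the SAP assesses modification by four continuous characteristics through two-level strata only. If modification is roughly linear and the covariate approximately normal, this loses about 36% to 66% of the interaction information for a smaller group of 50% down to 10%, and more if the smaller group is below 10%. These shares and shapes are assumptions.

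It would go too far to say that cutting has no benefit for the test, because a true step at the cut reverses the comparison. The stratum-size condition leaves the age, BMI and HbA1c analyses open to being dropped on an unstated criterion, but not the SBP analysis. The primary test, its alpha and the sample size are unaffected.

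**What to change.** In the SAP section on pre-specified subpopulations:

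1. Pre-specify a treatment-by-visit-by-continuous-covariate interaction for age, BMI, HbA1c and baseline SBP, linear with a quadratic or spline check, run whatever the stratum counts.
2. Name it as the effect-modification test for age, BMI and HbA1c, and keep the listed cut points for stratum-specific estimates.
3. For baseline SBP, keep the randomisation-stratum analysis and report the continuous term alongside it.
4. State the minimum number per stratum below which a stratum-specific estimate will not be given.
5. Leave sex, meal preparer status and family size as they are.

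The cost is a few sentences and four extra model terms, with no new data. The downside is a linearity assumption, which the non-linearity check and the retained stratum estimates cover.

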#### 3.4 Sensitivity analyses

In our primary analysis, we will include all measurements performed within the intended 3-month visit window, including those from participants with medication changes and

those with only one of the intended two sets of triplicate measurements over two visits at 3-months post-randomization. To address these situations, we have pre-specified the following sensitivity analyses.

#### Medication changes

First, in sensitivity analyses, we will exclude all participants with any antihypertensive medication change during the study period.

Second, we will tabulate and report the number with changes in antihypertension medication by direction of change (increase/start, decrease/stop, no change) according to intervention assignment.

Third, we will add 10 mm Hg (systolic) and 5 mm Hg (diastolic) to their follow-up visit measurement for those who started or intensified hypertension treatments. Conversely, for those with a reduction or cessation in antihypertensive medications we will subtract 10 mm Hg (systolic) and 5 mm Hg (diastolic) from the follow-up visit measurement. This approach has been adopted by others. We will also use the approach described by Law et al, i.e., adjustedsystolic =  $1.11*[systolic blood pressure] - 7.00 and adjusteddiastolic = <math>1.12*[diastolic blood pressure] - 5.81.^{6,7}$ 

Fourth, we will calculate the hypertension daily dose, using the approach by Min et al to examine the effect of the intervention on treatment intensity. The hypertension daily dose is a continuous variable, but we anticipate it will require log-transformation.

#### Protocol deviations in the number of blood pressure measurements

In sensitivity analyses, we will exclude those with protocol deviations in blood pressure measurement, specifically having only 1 of the 2 intended triplicates measures at 3-month follow-up visits.

#### Protocol deviations in the timing of blood pressure measurements

In sensitivity analyses, we will include those excluded from the primary analysis for having measurements outside the intended visit window (i.e., <105 days of when the intervention started).

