- Follow-up Visit 1 (FV1a & FV1b) This includes 2 in-person assessments that will be performed at the CRC or Bowdoin Street Health Center, 3 months post-randomization. FV1a includes a food insecurity screener, assessment of current medications, a rapid food frequency questionnaire, the SHoPPER questionnaire (on shopping habits, meal preparation, and dining behaviors), and a dietary symptom questionnaire. In addition, we will measure weight, perform phlebotomy, and perform an office BP measurement. Participants will be provided with a 26-hour ambulatory BP monitor and a 24-hour urine collection kit (to be dropped off at the CRC 1-2 days later at FV1b). FV1b will include a participant self-reported health form (short form health survey), a 26-hour ambulatory BP monitor and 24-urine collection form drop off forms, a perceived stress questionnaire, a post intervention knowledge assessment questionnaire, an office BP measurement, as well as repeat weight measurement. Those who do the DASH grocery intervention will be asked about diet compliance and palatability. FV1b will also include a 24-hour recall that coincides with the 24-hour urine timeline.
- Follow-up Visit 2 (FV2a & FV2b) This includes 2 in-person assessments that will be performed at the CRC or Bowdoin Street Health Center, 5-6-months post-randomization (equivalent to 2-3 months after the intervention). FV2a includes a food insecurity screener, assessment of current medications, a rapid food frequency questionnaire, the SHoPPER questionnaire, and a dietary symptom questionnaire. We also will measure weight and BP and perform phlebotomy. Participants will be fitted with a 26-hour ambulatory BP monitor and 24-hour urine collection kit (dropped off at the CRC 1-2 days later at FV2b). FV2b will also include a 24-hour recall that coincides with the 24-hour urine timeline, perceived stress scale questionnaire, and short-form health survey 1. In addition, 45 participants (35 from the DASH group and 10 from the self-directed group) will be randomly selected to participate in comprehensive qualitative interviews to characterize facilitators and barriers to DASH adoption ("Post-Intervention Maintenance Phase Qualitative Interviews"). The total number may be reduced or increased based on theme saturation (see Qualitative Interviews section below).

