## 1 Introduction

GoFresh is an individual level, randomized feeding trial to determine the effect of 12 weeks of dietitian-assisted DASH-patterned grocery shopping on seated blood pressure in 150-176 adults in the ages of 18-100 years. Participants are randomly assigned to one of 2 groups: (1) Dietitian-assisted, DASH-patterned grocery shopping or (2) Self-directed grocery shopping group. The trial is organized into two phases: the intervention phase (assessed at 3 months) and the observation (maintenance) phase with physical assessments at 6-months and behavioral assessments at 6 and 12 months. The primary trial analysis described in this document focuses on physical assessments at 3 and 6 months. Other outcome assessments performed during the study (i.e., qualitative interviews as well as questions related to quality of life, grocery shopping and dining habits, and perceived stress) are not planned as part of this analysis.

The **primary outcome** is the net effect of DASH groceries with reduced sodium, DASHpatterned groceries versus self-directed grocery shopping on 12-week seated systolic blood pressure (as measured at 3 months, the end of the intervention phase).

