## 5 Missing data

We will employ a number of recommended strategies to prevent missing data:

- A simplified data collection schedule that minimizes participant burden;
- Intention-to-treat analysis that includes following participants according to the data collection schedule regardless of compliance with the study intervention;
- Frequent engagement with the participants through visit reminder calls or notes;
- Contiguous windows of time during which specific follow-up visits are allowed;
- Monetary incentives to encourage enrollment and continued participation;
- Rigorous training of clinic staff emphasizing the importance of
  - Positive and warm interpersonal relationships between the participants and study staff
  - Study commitment during the consent process to ensure that potential participants understand the importance of completing the study
  - $\circ$   $\,$  Addressing participant concerns to minimize dissatisfaction  $\,$
  - $\circ$   $\,$  Collecting data even if a participant discontinues the study treatment
  - Reasons for any drop-outs will be documented.

We will perform the following sensitivity analyses using established methods for addressing missingness in clinical trials: use of out-of-window blood pressure measurements, multiple imputations at the individual level, and best and worst-case scenarios. We will compare the results from these approaches with primary analysis results to assess the primary result's robustness to the effects of missing data. Further, we will compare the baseline characteristics of complete cases and participants with missing measures between the two assignments.

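### Does the <105-day limit on 3-month blood pressures, counted from an undefined intervention start, put the primary analysis at risk?

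*SAP*

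**What the plan says.** SAP section 1 defines the primary outcome as "12-week seated systolic blood pressure (as measured at 3 months, the end of the intervention phase"). Section 3.2 adds: "We will perform an intent-to-treat analysis".

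SAP section 3.4 (Sensitivity analyses) says that for the primary analysis "we will include all measurements performed within the intended 3-month visit window", including readings from people whose medication changed and from "those with only one of the intended two sets of triplicate measurements over two visits at 3-months post-randomization". Its paragraph on timing then plans a sensitivity analysis that will "include those excluded from the primary analysis for having measurements outside the intended visit window (i.e., <105 days of when the intervention started").

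SAP section 5 lists, among measures to prevent missing data, "Contiguous windows of time during which specific follow-up visits are allowed". Its sensitivity analyses for missing data are "use of out-of-window blood pressure measurements, multiple imputations at the individual level, and best and worst-case scenarios".

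Protocol section 7 describes Follow-up Visit 1 as follows: "This includes 2 in-person assessments that will be performed at the CRC or Bowdoin Street Health Center, 3 months post-randomization". Follow-up Visit 2 is set at 5 to 6 months, also from randomisation. Protocol section 11 (Extension Period) lets a participant who misses weeks continue, in general, to week 13 or 14.

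**The concern.** Three features look like faults.

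- **Exclusion on a post-randomisation date.** Observed primary-outcome readings leave the headline estimate because they came late. If lateness differs by arm, the comparison could shift. Extensions follow missed intervention weeks, so a difference is plausible.
- **Undefined clock.** The window runs from the start of the intervention, which is not dated in either arm. The DASH arm has a first ordering session with no stated interval from randomisation. The self-directed arm has stipends at weeks 4, 8 and 12 but no named start event. Two analysts could select different readings, and the cut-off could differ by arm.
- **Apparent gap.** The 3-month window closes after day 104 and the 6-month visit opens at 5 months, yet section 5 speaks of contiguous windows.

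At stake is which readings enter the primary 3-month estimate. The remedy that suggests itself is to count every Follow-up Visit 1 reading taken before month 5 in the primary analysis and to make the 105-day limit the sensitivity analysis.

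**Working it through.** **1. The plan's own power figure.** Inputs from SAP 3.3: 75 per arm, difference 5.8 mm Hg, SDs 11.85 and 11.4, two-sided alpha 0.05. Pooled SD = √((11.85² + 11.4²)/2) = 11.63. Power from the noncentral t distribution is 0.859, against 0.85 stated. The plan's figure is reproduced, and 176 × 0.85 = 149.6, so 75 per arm is already net of attrition.

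**2. Where day 105 falls.** 105/7 = 15 weeks. A 12-week course ends on day 84 and one extended to week 14 on day 98. The window therefore allows 12 + 2 + 1 weeks. Three months is about day 91, so the planned visit lies well inside it.

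**3. Reading the clock.** The measurement schedule in Protocol section 7 places the randomisation visit at month 0 and the grocery ordering calls at months 0 to 3, labelled as intervention phase. Protocol section 7 (Randomization Visit) and section 10 have participants receive instructions for their assignment once randomised. SAP 3.4 itself describes the paired 3-month visits as post-randomisation. These all point to randomisation as day 0 in both arms. A cut-off that differs by arm needs DASH counted from the first order and controls from randomisation, which no text says. On that reading, with a first order 3, 7 or 14 days after randomisation (assumed), the last in-window day in DASH would be 104 + 3 = 107, 104 + 7 = 111 or 104 + 14 = 118, against 104 in controls.

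**4. The gap.** Five months = 5 × 365.25/12 = 152.2 days, and 152 − 105 = 47 days. This subtracts a limit counted from intervention start from a date counted from randomisation, so it is exact only if the two coincide. With a start lag of 3, 7, 14 or 21 days (assumed) the gap is 44, 40, 33 or 26 days. The section 5 bullet is about when visits are allowed; section 3.4 is about which readings enter one analysis. Both can hold.

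**5. What moving late readings into the primary analysis would do.** Let p be the late share in an arm and D the late-minus-in-window SBP difference in that arm. Including late readings changes the between-arm difference by p(DASH) × D(DASH) − p(control) × D(control). The documents give no p or D, so all values here are assumptions.

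- *Same D in both arms.* The change is the difference in late shares times D. For 5, 10 or 15 percentage points it is 0.15, 0.30 or 0.45 mm Hg at D = 3, and 0.29, 0.58 or 0.87 mm Hg at D = 5.8. With equal late shares it is 0.
- *Effect fading after the groceries stop.* Take 10% late in both arms and D(control) = 0. If half the 5.8 mm Hg effect has gone, D(DASH) = 2.9 and the expected difference falls to 5.8 − 0.10 × 2.9 = 5.51. If all has gone, it falls to 5.8 − 0.10 × 5.8 = 5.22.

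Power by the same formula:

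| Handling of 10% late readings | n per arm | Difference (mm Hg) | Power |
|---|---|---|---|
| Excluded | 68 | 5.80 | 0.823 |
| Included, half the effect gone | 75 | 5.51 | 0.822 |
| Included, all the effect gone | 75 | 5.22 | 0.780 |

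If 5% or 15% were late and excluded, power would be 0.839 (71 per arm) or 0.800 (64 per arm). These losses are stacked on the full 15% attrition, which is itself an assumption.

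**6. How far past the intervention.** Day 151 is 151 − 84 = 67 days after a week-12 finish, about 2.2 months. The protocol describes Follow-up Visit 2 as 2 to 3 months after the intervention. The latest readings counted as 3-month under the wider window would overlap that range and blur the planned 3- versus 6-month contrast.

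**The case for a change.** The strongest case for a change is the clock. The start of the intervention is nowhere defined, and an analysis that restores out-of-window readings inherits the same uncertainty, because what counts as out of window depends on day 0. Sensitivity analyses can expose a problem but leave the headline estimate as it is. Lateness may well be unequal: a week-14 finish leaves only days 98 to 104 for two clinic visits, and the extension rule, with its missed calls and modules, fits the DASH arm far better than the control arm.

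Much of this stands as description: the anchor is missing and unequal lateness is possible. It does not show that the window is wrong. A prespecified window is compatible with intention to treat, and the late readings return in the analyses of sections 3.4 and 5. Nor would equal lateness make the choice harmless, since the shift is zero only if late readings differ from timely ones by the same amount in both arms. Fading of the diet effect would break that condition, and it would count against including the late readings.

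One wording point also stands: the timing paragraph can be read as excluding people, whereas the opening of section 3.4 works measurement by measurement and keeps those with a single triplicate. The opening text settles how to read it.

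**Conclusion.** No change to the plan follows. The undefined start is a gap that analysts would fill with randomisation, on the strength of the visit schedule and the instructions both arms receive that day. The 105-day limit is a fair choice for an outcome defined at the end of the intervention. A wider window trades a modest loss of readings for possible dilution: at 10% late, power is 0.823 with exclusion against 0.822 to 0.780 with inclusion when half to all of the effect has faded. With less fading, inclusion would do somewhat better, so statisticians could reasonably differ. The gap of 26 to 47 days (start lag 21 to 0 days) is an interval between an analysis limit and a scheduled visit, and no contradiction with section 5 is shown.

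The conclusion rests on assumed late shares, start lags and degrees of fading, since the documents give none. The size and direction of any bias are therefore unknown. The planned out-of-window, multiple-imputation and best/worst-case analyses are there to show whether late readings matter.
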